Will group counseling sessions be difficult to coordinate among multiple women? Our team has successfully coordinated group counseling sessions as a part of the original Friendship Bench intervention,²⁴ and among postnatal women.³² Uptake of group counseling sessions has been very high and it has been feasible to integrate the group counseling sessions into routine clinical care.

What other retention support is available to HIV-infected women and how will this influence this study? During this pilot phase, we will carefully record what other retention support is available to HIV-infected women at the study sites and other area clinics, and how frequently women access these services. Currently at our five sites these services consist of tracing patients who have defaulted for >2 months. Tracing is done either by clinic personnel, depending on available MoH funding for transportation, or by staff of the local NGO Lighthouse Trust through PEPFAR and CDC funding. A time-updated understanding of available retention support services will be critical in order to design the subsequent RCT to test the effectiveness of the Friendship Bench in improving PND and engagement in HIV care.

G. Timeline for Work Plan

Timeline	2019					2020				2021	
	Aug	Sep	Oct	Nov	Dec	Q1	Q2	Q3	Q4	Q1	Q2
Continued planning and development											
Post job openings and hire staff											
Staff training											
Launch 3-arm pilot trial											
Pilot accrual and follow-up; Fidelity monitoring											

Exit Interviews											
Data analysis, manuscript preparation, RCT planning											

H. Dissemination of Results

Results from this study will be shared with the Community Advisory Board at UNC-Project and other key stakeholders, including HIV-infected women, community members, HIV and mental health providers, the National Health Sciences Research Committee, and Ministry of Health officials in Malawi. We will also disseminate our results through presentation at international scientific conferences focused on HIV, mental health, or women's health and through publication in peer-reviewed journals.

I. Impact and Future Directions: PND is extremely common in sub-Saharan Africa and negatively affects women, infants, and communities. For HIV-infected women, PND may also adversely affect perinatal engagement in HIV care, putting them at an even greater risk of poor HIV outcomes. Resource-appropriate interventions to address PND, and its possible impact on engagement in HIV care, are urgently needed. The information gathered in this proposal will lead to an R01 application to test our intervention in a randomized controlled trial.

J. Protection of Human Subjects

This Human Subjects Research meets the definition of clinical research. The data collection and analyses outlined in this proposal will be reviewed by the University of North Carolina Institutional Review Board, in the U.S., and the Malawi National Health Sciences Research Committee (HSRC) before any data collection or analysis occurs.

The study will also be reviewed and informed by the existing community advisory board (CAB) of UNC Project in Malawi. The CAB will review the study protocol prior to implementation and provide feedback. The CAB meets monthly.

1. Risks to Human Subjects

a. Human Subjects Involvement and Characteristics

In our pilot study, we will recruit 92 prenatal HIV-infected women who consent to participate and screen positive for mental health disorders during pregnancy on the EPDS or SRQ-20 questionnaires, indicating perinatal depression (PND) or common mental health disorders. Psychosocial counselors (n=4), research assistants (n=3), and supervisors (n=2) will be considered a secondary population. The goal of our study is to evaluate the feasibility, acceptability, and fidelity of the enhanced Friendship Bench intervention to improve PND and engagement in HIV care among HIV-infected women. Women will be recruited from the Lumbadzi, Mitundu, Nathonje, Area 18, and Bwaila healthcare centers in Lilongwe, Malawi when they present for prenatal care initiation and are HIV-positive. All women who screen positive for depression will be referred for mental health treatment to the nearest provider.

Rational for including pregnant women: Option B+ is a program of the Malawi Ministry of Health to provide lifelong ART to all HIV-infected women who are pregnant. A critical component to the success of Option B+ is keeping women engaged in HIV care – something that has emerged as a challenge since Option B+'s inception in Malawi. Women with PND may be at an increased risk of disengaging from HIV care. Our project includes pregnant women in an effort to improve treatment options for PND among this population, with the goal of also improving engagement in HIV care and ultimately the effectiveness of Option B+.

The study characteristics of the study population are expected to be similar to those of all HIV-infected, peripartum women with PND in public healthcare centers in Lilongwe, Malawi.

Participants who live outside of the Lilongwe District or are less than 18 years old will be excluded.

b. Sources of Materials

All data will be gathered specifically for the purpose of the study. For Aim 1, women will undergo a screening and enrollment visit (baseline), up to six counseling sessions, and will have outcomes assessed at 6 months.

Screening and Enrollment HIV-infected women who are initiating, re-initiating, or continuing ART during pregnancy under the Option B+ will be informed about the study by their provider and invited to participate. Screening and enrollment procedures will take place on the same day as a woman's ANC visit. Women who consent to participate (Appendix 1) will be given an initial screening for perinatal depression or anxiety using the Patient Health Questionnaire (PHQ)-2 and/or the Generalized Anxiety Disorder (GAD)-2 as a part of routine antenatal care. Women who show symptoms perinatal depression or anxiety will be asked to complete the Edinburgh Postnatal Depression Scale (EPDS) and/or the Self-Reporting Questionnaire (SRQ)-20 with a trained psycho-social counselor to confirm symptoms (Appendix 2). Women who screen positively on either the PHQ-2/GAD-2, the EPDS (≥ 10), or SRQ-20 (≥ 8) will be invited to participate. Women screening positive for depression who choose not to participate will be referred to a mental health provider for care.

Study Visits (n=2 for participants in all arms)

Baseline Visit: At the baseline visit, women will be asked to fill out a questionnaire about their mental health, HIV, and reproductive health history. In addition to assessing depression with the EPDS, we will assess the prevalence of common mental disorders using the Self-Reporting Questionnaire (SRQ-20). The SRQ-20 was designed by the World Health Organization as a screening tool for common mental health disorders (CMD). The SRQ-20 has 20 questions exploring symptoms of depression, anxiety and somatic complaints, rather than a specific diagnosis of depression or anxiety. The SRQ-20 was validated in Malawi and is available in Chichewa.^{50,51} A cut-point of 8 or above has been previously used in Malawi to identify probable CMD. The baseline interview will also assess socio-demographics, self-reported health, and key structural and psychosocial factors including trauma history, intimate partner violence (IPV), other violence in the home, socioeconomic measures, coping, social support, self-efficacy, and experiences of stigma related to HIV and mental health (Appendix 2). Measures of trauma, IPV, and other violence will be important for understanding participants' experience of depression in their broader socioecological context. We have used these measures previously in similar settings.

6-month Postpartum Visit: At 6 months postpartum, HIV-infected women will be asked to complete the EPDS and SRQ-20, either in person or by phone. Viral load measures for all HIV-infected women will be collected by study personnel at 6 months postpartum. Information on HIV appointment attendance, infant birthweight, and infant HIV testing during the first 6 months postpartum will be collected from a participant's medical record, as we are doing in our ongoing USAID project. Information on infant anthropometry (length, weight, head circumference), infant physical health (presence of respiratory illness, diarrhea, and immunization records) and infant development, assessed using the Observation of Mother-Child Interaction guide, the PAMANED Study Family Care Indicators Questionnaire in Chichewa, and the WHO Indicators of Infant and Young Child Development (IYCD) Item guide, which have been validated for use in children as young as 4 months of age, will also be collected (Appendix 2). HIV-infected women, counselors and supervisors will be asked to complete a brief exit interview, either in person or by phone, to assess the feasibility and acceptability of the intervention.

Counseling Sessions (EFB n= up to 7; ESC, n=0):

Women will be followed from ART initiation through 6 months postpartum. Women in the EFB arm will receive approximately 4 prenatal individual counseling sessions and approximately 2 optional, but recommended postnatal group counseling sessions (n=up to 6 counseling session). Women in the EFB arm will receive an additional social support session described in section F6 (n=up to 7 counseling sessions). Women in the ESC arm will not receive counseling sessions, but will receive psychoeducation from a trained research assistant, referrals as needed, and follow-up calls to assess whether referrals were acted on and whether any further unmet mental health needs remain (n=0 counseling sessions). Counseling sessions will take place every 1-2 weeks at the antenatal care clinic, or via phone, during the prenatal period and approximately monthly during the postnatal period to coincide with routine ART refill visits.

Data Collection: At each counseling session (prenatal and postnatal) women will be asked to complete the

EPDS and SRQ-20 to assess their mental health status^{50,51}

All data will be collected by trained research assistants and stored in a database on the secure UNC Project Server, which only the PI will have access to. For each aim, participants will be assigned a study identification number. This study identification number will be linked to their name and clinic site through a separate log book. The log book will be kept at UNC Project's offices in a locked cabinet. At the conclusion of the study the link between the participant's name and study number will be destroyed. The principal investigator will be the only person with access to the subject identities.

c. Potential Risks – Including for Pregnant Women

Potential risks to the study population include loss of confidentiality and social harms to participants. Loss of confidentiality could include disclosure of HIV status. Social harms include emotional harm, economic or financial harm to the participant related to a woman's HIV or PND status being disclosed. While study participants will be pregnant at baseline, we do not anticipate any additional risks to women or their fetuses by being involved in the study. Procedures to protect against these risks are described below.

2. Adequacy of Protection against Risks

a. Recruitment and Informed Consent

The research study will be described briefly to all women initiating, reinitiating, or continuing ART at Lumbadzi, Mitundu, Nathonje, Area 18, and Bwaila healthcare centers in Lilongwe while they wait in the reception area. Once a participant is determined to be eligible for the study and following the standard post-test counseling, a trained interviewer will complete an informed consent process with each participant in their native language, Chichewa. During the informed consent process, the counselor will describe the procedures to be followed, the risks and benefits of participation, the duration of participation, and the steps taken to protect participant's confidentiality, particularly with respect to keeping all personal and private information (such as HIV and PND status) private. Illiterate participants may sign the consent form via thumbprint, in the presence of an impartial witness (Appendix 1). Any questions or concerns about privacy will be answered by the counselor or referred to the PI, who will address them. HIV-infected women initiating, reinitiating, or continuing ART prenatally who screen positive for perinatal depression or anxiety on the PHQ-2, GA-2, EPDS (≥ 10) or SRQ-20 (≥ 8) measure, and who consent to participate will be enrolled. All women who screen positive for PND will be referred to outpatient psychiatry services that are currently available and staffed by master's level nursing staff that can prescribe antidepressant medications.

Written informed consent will be obtained from each participant and participants will be provided with a copy of their informed consent forms if they are willing to receive it (Appendix 1). Study staff will document the informed consent process.

b. Protection against Risk

Risks of loss of confidentiality or social harms to participants will be minimized by: 1) training of study staff in the ethical conduct of research; 2) strict protection of confidentiality and personal information; 3) close monitoring of social harms with appropriate IRB reporting.

Discussing personal information – Data collection will include asking women about their mental health, social support, alcohol use and intimate partnerships. All data associates will be trained to keep all information confidential. Research assistants will be trained, and participants informed, that they can pause or discontinue a research interview at any time if they find the topic upsetting.

Data security - All study data, including interview guides, audio recordings of interviews, interview transcribes, and logbooks will be kept in a locked cabinet at the UNC Project data center, where they will be maintained in a locked office at UNC Project accessible only to the principal investigator. Interviews that are transcribed and computerized will be stored on the secure central server at UNC Project. For analysis purposes, data will be de-identified before coding and analysis. Only the principal investigator, data entry personnel, and assigned data analysts will have access to the de-identified electronic study database. Video recordings will be

transferred onto the OneDrive secure server with access restricted to study personnel, where they will be reviewed to verify the accuracy of the interviewer rating.

Home visits for women - For women who receive home visits as part of the EFB, information on the participant's HIV status or the nature of the home visitor's interest in visiting the participant will not be disclosed. All women presenting to HIV clinic sites and accepting the services are considered fully protected by the policies and guidelines outlined in the Government of Malawi's 'National HIV/AIDS Policy, October 2003', 'HIV/AIDS Counseling and Testing, Guidelines for Malawi, Second Edition, 2004'. No participants will be identified in any report or publication about this study.

3. Potential Benefits of the Proposed Research to the Subjects and Others

This study has some minimal risks associated with participation and we anticipate that few participants will experience negative events as a result of taking part in the study. This research will improve our understanding of how an adapted and enhanced counseling intervention may improve PND and engagement in HIV care. Long-term, supporting HIV-infected women with PND through a counseling intervention carried out by counselors is expected to reduce PND, improve engagement in HIV-care, and ultimately improve women's health and HIV outcomes. Therefore, the risk to individual participants in the study is small and the potential benefit to society is substantial.

Individuals participating in study research interview visits will receive a transport reimbursement of 7,000 Malawian kwacha (about US\$10) at the completion of the baseline and 6-month interviews. Individuals participating in counseling sessions will receive a transport reimbursement of 3,500 Malawian kwacha (about US\$5) at the completion of each counseling session.

4. Importance of the Knowledge to be Gained

This project will provide important information about whether an adapted and enhanced counseling intervention is a feasible and acceptable strategy to improve PND and engagement in HIV care among HIV-infected women. Disengagement from HIV care is a critical issue among women taking ART under the Option B+ program. In the general HIV-infected population, depression has been identified as an important detriment to retention in HIV care. Rates of PND are high among HIV-infected women in Malawi. However, the importance of addressing PND in the context of retention in care support has received little attention. The proposed project builds on formative research on women and healthcare providers' experiences with and preferences for treating PND among HIV-infected women through qualitative interviews, and uses that information to launch a pilot study testing culturally-adapted and enhanced forms of an existing, evidence-based counseling intervention to treat PND and support engagement in HIV care among HIV-infected women.

5. Data Safety and Monitoring Plan

This project involves a pilot randomized controlled trial compared the Adapted Friendship Bench and Enhanced Friendship Bench interventions, to enhanced standard care, to address PND and engagement in HIV care in HIV-infected women. Participation in the study involves sharing possibly personal or sensitive information, such as HIV-status and experiences related to PND. In order to keep participant's private information and identity safe, we will store all data on a secure server at UNC Project in Malawi, which only the PI will have access to. In addition, to prevent any unforeseen risk we will also provide all participants with study contact information and ask that they contact us immediately if they experience any social harm or other adverse event, such as disruption of families, acts of discrimination or physical harm. If a social harm is reported, a short questionnaire will be administered to characterize the social harm and describe its impact. All reported social harms will be documented and communicated to the Malawi Health Science Research Committee (HSRC) and the UNC Institutional Review Board within 7 days.

H. Budget

Line Item	Cost per unit (USD)	# and type units	Total Cost
1. Study Staff			
Counselors	\$200	4 x 12 months	\$ 9,600
Research assistants*	\$200	3 x 12 months	\$7,200
Sub-total			\$ 16,800
2. Compensation for study participants			
Study visit travel reimbursement	\$10	105 participants x 2 study visits (baseline and 6-month follow-up visit)	\$2,100
Counseling session travel reimbursement	\$5	35 AFB participants x 6 counseling sessions; 35 EFB participants x 7 counseling sessions	\$2,275
Sub-total			\$4,375
3. Other Research Costs			
Paper, toner, and printing costs			\$1,000
Fuel for study activities			\$500
Airtime for study staff			\$525
Tablets for data collection			\$500
Translation Fees			\$200
Malawi IRB Fee			\$150
Sub-total			\$2,875
Total			\$24,050
10% NHSRC fee			\$2,405

*Research assistants will float between clinics as needed to meet project needs.

I. BUDGET JUSTIFICATION

PERSONNEL

Counselors in Malawi (\$9,600 - 100% effort for 12.0 months) – Four counselors (2 per intervention clinic) will be hired to conduct pre- and post-natal counseling sessions and home visits for HIV-infected women over a 12 month period. \$200 salary/month x 4 counselors x 12 months = \$9,600.

Research Assistants in Malawi (\$7,200 -100% effort for 12.0 months)- Three research assistants will be hired to conduct mental health screening with the Edinburgh Postnatal Depression Scale and Self-Report Questionnaire-20 and to complete data collection for study visits over a 12 month period. \$200 salary/month x 3 RAs x 12 months = \$7,200.

Total Personnel Costs \$16,800

COMPENSATION FOR STUDY PARTICIPANTS

Study Interview Travel Reimbursement (\$2,100) – A total of 105 participants will be included in our proposed aim. Each participant will receive 7,000 Malawi Kwacha (~\$10/person) as an incentive to participate in the study for each study visit. $\$10 \times 105 \text{ participants} \times 2 \text{ visits (baseline and 6 months)} = \$2,100$.

Counseling Session Travel Reimbursement (\$2,275) - Participants in the EFB arm (n=up to 6 counseling sessions) and the AFB (n=up to 7 counseling sessions) will also receive travel reimbursement as an incentive to attend intervention counseling sessions. $35 \times 5 \times 6 = \$1050 + 35 \times 5 \times 7 = \$1,225$, for a total of \$2,275.

Total Compensation for Study Participants Costs \$4,375

OTHER RESEARCH COSTS

Paper, toner and printing costs (\$1,000) – We have budged \$1000 to cover the costs of paper, toner, and printing costs for all study material, including informed consent forms, screening and enrollment logs, and logs for counselling sessions.

Fuel for study activities (\$500) – We have budged \$500 to cover the costs of fuel for study-related activities, including getting staff to and from study sites and for home visits.

Airtime for study staff (\$525) – We have budged \$500 to cover the costs of airtime for study staff so they can be in contact with one another as needed and with the project coordinator.

Tablets for data collection (\$500) – We have budged \$500 to purchase 3 tablets (\$167 x 3 tablets) to support data collection activities.

Translation and Transcription Fees (\$200) – All study materials including informed consent forms, in-depth interview guides, and the Edinburgh Postnatal Depression Scale will be translated into Chichewa, the local language in Lilongwe, Malawi. Translation fees \$200.

Malawi IRB Fee (\$150) – All research in Malawi must receive ethical approval from the National Health Science Research Committee, which charges a \$150 fee to review all applications for ethical approval.

Total Other Research Costs \$2,875

TOTAL COSTS: \$24,050

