[name], psychiatrist who has collaborated on several studies of mental health integration in Malawi. The team further includes **[name]**, Scientific Director at UNC Project-Malawi, **[name]**, psychiatrist at the University of Zimbabwe, developer of the Friendship Bench and a leader in developing task-shifting models for treating mental health disorders in low-income countries; **[name]**, Malawian psychiatrist leading mental health reform efforts in Lilongwe; and **[name]**, Assistant Director of Clinical Mental Health Services at the Malawi Ministry of Health. These team members have all collaborated together previously on mental health research and service initiatives in Malawi. Overall this impressive and experienced team is well positioned to successfully implement this high-impact project.

F2. Study Design: We will conduct a clinic-level pilot study among five clinics. Three of the five clinics initially served as primary study sites and were assigned to one of 3 conditions: 1) Adapted Friendship Bench (AFB; n=1 clinic/35 women), 2) Enhanced Friendship Bench (EFB; n=1 clinic/35 women) or 3) Enhanced Usual Care (n=1 clinic/35 women).

In June 2020, it was clear that due to both low patient volume and COVID-19 delays, recruitment targets would not be met at these three sites. Therefore recruitment is on hold at these sites and resources will be focused on launching activities at two new larger sites: Bwaila and Area 18. These sites will employ individual-level randomization of the study intervention. Participants will be enrolled at an ANC visit prior to or including 34 weeks gestation and followed through 6 months postpartum.

F3. Study Setting and Site: The proposed study will be conducted at five public antenatal clinics in Lilongwe District, Malawi: Lumbadzi, Mitundu Nathenje, Area 18, and Bwaila health centers. Each of the five health centers provides ART services to HIV-infected women through the antenatal clinic during pregnancy, and also has separate ART clinics serving non-pregnant HIV-infected adults on the health center grounds. In Malawi, HIV-infected pregnant women typically initiate ART at an antenatal care clinic, and transition to an HIV clinic for care after delivery. Thus, the co-location of antenatal and ART services makes these health centers the ideal locations to serve HIV-infected women as they transition from receiving HIV care prenatally in an antenatal clinic, to postnatally in an ART clinic.

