In Malawi, all pregnant women presenting for care receive opt-out HIV testing at their first antenatal care visit. Women who test HIV+ undergo adherence counseling and start ART the same day. PND screening and assessment are rare to nonexistent at antenatal/ART clinics in Lilongwe, as in most clinical settings in Malawi.

UNC Project in Lilongwe will serve as the administrative home for the study and has longstanding relationships with Bwaila FHU, antenatal/ART clinics in Lilongwe, and the Ministry of Health.

F4. Study Population:

Women (92 total): As of this protocol v3.2, we have recruited a total of 12 women from our original 3 clinics. As we launch activities at our two new clinics and reduce to 2 arms, we will seek to recruit 40 new participants per arm or 80 new participants total, for a total enrollment of 92 participants. All 92 women will contribute to analyses of feasibility and acceptability, but only the new 80 women will contribute to between-arm comparisons due to the differences in sites.

We will include 92 HIV-infected, depressed women initiating, re-initiating, or continuing ART who engage in ANC and are identified with antenatal depression at ≤ 34 weeks gestation to allow sufficient time for approximately 4 prenatal counseling sessions and approximately 2 postnatal counseling sessions. Women with a score ≥ 10 on the EPDS^{48,49} and/or ≥ 8 on the SRQ-20 will be considered to be depressed and will be invited to participate.

Inclusion criteria:

- HIV-infected, pregnant women initiating, re-initiating, or continuing ART during antenatal care (ANC)
- ≤ 34 weeks gestation to allow sufficient time for approximately 4 prenatal counseling sessions and approximately 2 postnatal counseling sessions.

- Screened positive for depression with a score ≥ 8 on the SRQ-20
- At least 18 years of age

Feasibility of recruitment – Approximately 30 HIV-infected women initiate or re-initiate ART monthly at each of the study sites, or 150 women over 6 months, with ~90% presenting at ≤ 30 weeks. Based on our group's systematic review³⁴, we conservatively estimate 30% of HIV-infected women will have antenatal depression, suggesting that enrolling ~6 women per site per month is feasible. Utilization of two additional clinics will aid in timely participant recruitment should enrollment at the three primary sites lag behind expected targets.

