Data Collection: At each counseling session (prenatal and postnatal) women will be asked to complete the EPDS and SRQ-20 to assess their mental health status.

F9. Outcomes – The primary goal of this R34 application is to evaluate the feasibility, acceptability, and fidelity of a counseling intervention to improve PND and engagement in HIV care among HIV-infected women. Recognizing the small sample size, indicators of preliminary effectiveness of the intervention for mental health and engagement in care outcomes will be reported as secondary outcomes. Primary and secondary outcomes will be assessed at 6 months postpartum and compared across the study arms.

F9.a. Primary Outcomes:

Feasibility will be defined as the ability to successfully enroll and retain HIV-infected, depressed women in the pilot intervention. Feasibility will be assessed as the number of women enrolled, a comparison of planned to actual enrollment and reasons for non-enrollment, and the proportion of women retained in each arm at 6 months postpartum.

Acceptability will be defined as the ability to deliver a culturally and resource-appropriate intervention. Acceptability will be assessed through brief exit interviews among a subset of HIV-infected women. Exit interviews will include both closed and open-ended questions and will assess how easy the intervention was to participate in or deliver, the perceived usefulness of the intervention, and suggestions for improvement.

Fidelity will be defined as adherence to the intervention protocol. Fidelity to session content for both individual and group counseling sessions will be assessed by members of the Friendship Bench team (DHO or study psychiatrist), by using a checklist of intervention characteristics either during direct monitoring or using audio recording of up to 3 randomly chosen sessions per counselors. Scoring either 'meeting expectations' or 'exceeding' expectations' on at least 80% of applicable checklist items during each session will be considered fidelity to the intervention protocol.

F9.b. Secondary Outcomes: Secondary outcomes will be used to provide preliminary information about effectiveness at 6 months postpartum, taking into consideration the limited sample size for the pilot project.

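### The enrolment part of the primary feasibility outcome is a head count compared between randomised arms, with no proportion of eligible women enrolled and no rate per site-month

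*Combined protocol and SAP*

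**What the plan says.** F9.a makes feasibility one of three primary outcomes, covering both enrolment and retention. On enrolment it states: "Feasibility will be assessed as the number of women enrolled, a comparison of planned to actual enrollment and reasons for non-enrollment". Retention by arm six months after delivery completes the definition. F10 then compares EFB with ESC on an average count of women enrolled and on the proportion retained. Neither section names a proportion of eligible women who enrol, a rate of enrolment over time, or a recruitment window.

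F4 and F11 set the target at 40 women per arm (80 new women), individually randomised at two new sites. With the 12 already enrolled the total is 92. F4 lets all 92 inform feasibility but restricts between-arm comparisons to the new 80.

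F4's recruitment estimate starts from "Approximately 30 HIV-infected women initiate or re-initiate ART monthly at each of the study sites", continues "or 150 women over 6 months, with ~90% presenting at ≤ 30 weeks", adds that "we conservatively estimate 30% of HIV-infected women will have antenatal depression", and ends by "suggesting that enrolling ~6 women per site per month is feasible". F2 explains the hold at the first three clinics by saying that "due to both low patient volume and COVID-19 delays, recruitment targets would not be met at these three sites". The budget justification covers the printing of "screening and enrollment logs".

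**The concern.** A pilot that must show that women can be enrolled needs to know how many could have enrolled and how long enrolment took. The measures in F9.a and F10 fix neither. The one enrolment comparison that F10 spells out is between arms, and arm sizes in an individually randomised phase are set by design.

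Sections B and F11 present the pilot as preparation for a large trial. To size and schedule it, that trial will need the screen-positive rate, the acceptance rate and the monthly yield per site. F2's account of the first three clinics shows the difficulty: the protocol gives no number screened, eligible or refusing, so a reader cannot tell how far the shortfall came from few eligible women and how far from refusal.

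**Working it through.** **1. The between-arm count.** Only the 80 individually randomised women enter between-arm comparisons (F4), with 40 planned per arm (F11). The expected difference in number enrolled is 40 − 40 = 0, whatever share of eligible women accept. Any departure reflects the allocation procedure. F10 also does not say over what unit (site, month) the average is taken.

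**2. F4's planning rate.** Inputs from F4: 30 women per site per month, 0.90 presenting early enough, 0.30 depressed.

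- Eligible per site-month = 30 × 0.90 × 0.30 = 8.1.
- Acceptance implied by about 6 enrolled = 6 / 8.1 = 74%.

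The stated 6 is therefore not reproduced without an acceptance rate that F4 does not give.

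F4's second volume figure does not match its first: 30 × 6 = 180, not 150. Read per site, 150 / 6 = 25 per month, so eligible = 25 × 0.90 × 0.30 = 6.75 and implied acceptance = 6 / 6.75 = 89%.

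**3. What the count shows if recruitment stays open until 80 are enrolled.** This is an assumption. The 40% and 20% rows are illustrative and come from no document. Two sites at 8.1 give 16.2 eligible women per month. With acceptance a:

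| a | Eligible women needed, 80/a | Not enrolled | Months, 80/(16.2a) | Final count |
|---|---|---|---|---|
| 74% | 108 | 28 | 6.7 | 80 |
| 40% | 200 | 120 | 12.3 | 80 |
| 20% | 400 | 320 | 24.7 | 80 |

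With 6.75 eligible per site-month (13.5 at two sites) the times are 8.0, 14.8 and 29.6 months. The count does not vary with acceptance; the proportion and the rate do.

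**4. What happens if recruitment closes at 12 months.** This window is also an assumption, borrowed from the 12-month staff funding in the budget. Enrolled = 16.2 × a × 12, which is 78 at 40% and 39 at 20%. Reaching 80 needs a = 80 / (16.2 × 12) = 41%. In that case low acceptance shows as a shortfall.

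**5. Precision of the missing proportion.** Half-width = 1.96 × √(a(1 − a) / (80/a)). At 74%: 1.96 × √(0.74 × 0.26 / 108) = 8.3 points. At 40% it is 6.8 points and at 20% it is 3.9. If the two sites contribute equally, the per-site half-widths are √2 times larger: about 11.7, 9.6 and 5.5 points.

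**The case against.** A reader might infer that the plan would report full success, 80 of 80, even if only one eligible woman in five agreed. The documents do not support that as a prediction. No section says that recruitment is open-ended. The timeline in section G ends in the second quarter of 2021 (its bars are not legible and it still describes three arms), and staff are budgeted for 12 months. On F4's own pool, one-fifth acceptance would leave a visible shortfall within 12 months. To reach 6 per site-month at 20%, a site would need 6 / 0.20 = 30 eligible women a month, 3.7 times the 8.1 that F4 implies. A larger pool is possible, because F2 calls the new sites larger and women continuing ART are eligible but not counted in F4's 30. Its size is not given.

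Three further points are fair:

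- Planned against actual enrolment did expose the problem at the first three clinics: 12 women against 3 × 35 = 105.
- Reasons for non-enrolment belong to the primary outcome. If a reason is recorded for every non-enrolled woman, they give at least a partial count and can help separate refusal from ineligibility.
- Retention, the other half of feasibility, does have a denominator.

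These points rule out the stronger reading but do not close the gap. F9.a and F10 do not say how reasons will be tabulated or over what total. Planned enrolment is not tied to F4's rate or to a date. Retention says nothing about enrolment.

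**Conclusion.** The point holds in limited form. The between-arm comparison of number enrolled cannot show ability to enrol, and this follows from the design without further assumptions. The absence of an enrolled/eligible proportion and a site-month rate is plain from F9.a and F10.

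The size of the hidden assumption is an acceptance of about 74%, or about 89% on the per-site reading of the six-month total. Both inherit F4's inputs, which use a 30-week share although the limit is 34 weeks, and which leave out women continuing ART. That the count is blind to acceptance is conditional on recruiting until the target is filled.

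The change should be made because it replaces an uninformative analysis of a primary outcome with one that the later trial can use.

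**What to change.** Reconcile three matters first, because they determine the denominators:

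- **Consent point.** F8 and section J.1.b place consent before screening; section J.2.a places it after eligibility is established.
- **Screening criterion.** F4's inclusion list names only the SRQ-20 threshold, while F8 also admits women positive on the EPDS or on the PHQ-2/GAD-2.
- **F4's two volume figures.**

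Then, in F9.a and F10, replace the between-arm comparison of number enrolled with the following, by site and with 95% confidence intervals:

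1. women enrolled / women screened positive and eligible;
2. women screened positive / women screened;
3. women enrolled per site per open month, set against the planned 6 or so.

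Tabulate reasons for non-enrolment as counts over the denominator of (1). If consent does precede screening, show refusals before screening on a separate line. Keep the number enrolled as a descriptor. Report the first three clinics on the same measures as far as their logs allow.

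The cost is wording in two sections and a tabulation. The logs must record refusals and dates, and the documents show only that printing them is budgeted. The reported figures may look less favourable than a count against target.
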